## 8.2 Assessment

### 8.2.1 Relevant Medical History

Relevant medical history, to include symptoms resulting from bladder cancer at the time of screening (not the bladder cancer diagnosis itself), will be collected and documented at the Screening Visit on the Medical History eCRF.

Date and stage of the first diagnosis of bladder cancer must be recorded in the Cancer History eCRF ONLY. Histology and supportive immunohistochemistry markers as well as relevant molecular markers, should be obtained when available and also documented on the Cancer History eCRF.

Detailed description of all bladder cancer treatments (including drug and non-drug therapies, surgeries, radiation therapies) with their corresponding start and stop dates should be recorded on the applicable eCRF (either the Prior Cancer Medication eCRF or the Non-Drug therapies eCRF), with special attention to first-line treatment for locally advanced or metastatic UC.

### 8.2.2 Prior and Concomitant Medication

All medication for concomitant diseases, except homeopathic substances and dietary supplements, must be recorded in the Prior and Concomitant Medications eCRF and the subject's medical record and should include information about the indication, dosage regimen, and onset and end of treatment.

The following medication, taken within 90 days of the screening visit, will also be recorded in the Prior and Concomitant Medications eCRF and the subject's medical record: vaccines, corticosteroids (via any route of administration), other immune-modulating drugs, immunoglobulin and/or any blood products, investigational drugs and depot preparations.

#### 8.2.2.1 Permitted Medications

Any medications prescribed for concomitant disease or symptomatic relief of current disease are permitted with the exception of the ones listed in [Section 8.2.2.2](#).

For clarification purposes, the following medications and therapies are also allowed:

Palliative radiotherapy for bone metastases or non-target soft tissue lesions completed > 7days prior to Screening imaging.

Hormone-replacement therapy or oral contraceptives.

Prophylactic antibiotics e.g., for prevention of urinary tract infection (UTI) or to prevent chronic obstructive pulmonary disease (COPD) exacerbation.

Influenza vaccination may be given during influenza season only (October – March) except live, attenuated vaccine (see [Section 8.2.2.2](#))

Prior non-experimental cancer vaccines and cellular immunotherapy indicated for superficial UC (for example Bacillus Calmette-Guérin [BCG]) or postsurgical adjuvant treatment of operable infiltrating UC.

The use of inhaled, nasal, ophthalmic and topical corticosteroids, physiologic replacement doses of glucocorticoids (i.e., for adrenal insufficiency) and mineralocorticoids (e.g., fludrocortisone for adrenal insufficiency).

The use of acute, low-dose, systemic corticosteroid medications (e.g., a one-time dose of dexamethasone for nausea or for prevention of hypersensitivity reactions to contrast agents).

### **8.2.2.2 Prohibited Medications**

The following medications are prohibited during the trial, as well as prior to Day 1 based on the relative type of medication. Additional medications may be deemed prohibited based on review during screening, if there is the risk to the subject or the ability to capture the trial outcome for the subject.

- Any approved or experimental anti-cancer therapy including chemotherapy within 3 weeks prior to Day 1, and throughout the trial.
- Treatment with any other investigational agent within 28 days prior to Day 1.
- Therapeutic oral or IV antibiotics within 1 week prior to Day 1.
- Live, attenuated vaccine including influenza vaccine (FluMist), within 4 weeks of Day 1 and throughout the trial.
- Prior treatment with CD137 agonists or immune checkpoint blockade therapies, including anti-CTLA-4, anti-PD-1 and anti-PD-L1 therapeutic antibodies and throughout the trial.
- Treatment with systemic corticosteroids or other systemic immunosuppressive medications (including but not limited to prednisone, dexamethasone, cyclophosphamide, azathioprine, methotrexate, and anti-TNF agents) within 2 weeks prior to Day 1 and throughout the trial, or anticipated requirements for systemic immunosuppressive medications during the trial.

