22. Any other diseases, metabolic dysfunction, physical examination finding, or clinical laboratory finding giving reasonable suspicion of a disease or condition that contraindicated the use of an investigational drug or that could affect the interpretation of the results or render the patient at high risk from treatment complications.
23. Prior treatment with CD137 agonists or immune checkpoint blockade therapies, including anti-CTLA-4, anti-PD-1, and anti-PD-L1 therapeutic antibodies
24. Treatment with systemic immunostimulatory agents (including but not limited to IFNs, interleukin [IL]-2) within 6 weeks or five half-lives of the drug, whichever was shorter, prior to Day 1.

25. Treatment with systemic corticosteroids or other systemic immunosuppressive medications (including but not limited to prednisone, dexamethasone, cyclophosphamide, azathioprine, methotrexate, and anti-tumor necrosis factor [anti-TNF] agents) within 2 weeks prior to Day 1, or anticipated requirement for systemic immunosuppressive medications during the trial
- a. Patients who receive acute, low-dose, systemic corticosteroid medications (e.g., a one-time dose of dexamethasone for nausea) or for prevention of hypersensitivity reactions to contrast agents may be enrolled in the trial.
  - b. The use of inhaled, nasal, ophthalmic, intra-articular, auricular or topical corticosteroids, physiologic replacement doses of glucocorticoids (i.e., for adrenal insufficiency), and mineralocorticoids (e.g. fludrocortisone for adrenal insufficiency) is allowed.

Statistical  
considerations

Simon's two-stage design ([Simon, 1989](#)) will be used within each cohort. Due to the multiple testing involved in having two cohorts, the individual cohort alpha has been set to 0.025 (one-sided) to ensure a trial-wide type I error rate of  $\alpha < 0.05$ .

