### 6.3 Atezolizumab (Tecentriq®)

Tecentriq® (atezolizumab) is a commercially available fully humanized, engineered monoclonal antibody of IgG1 isotype against the protein PD-L1 approved for the treatment of locally advanced or metastatic urothelial carcinoma that has progressed after platinum-containing chemotherapy.

The recommended dose of atezolizumab is 1200 mg administered as an intravenous infusion over 60 mins every 3 weeks. If the first infusion is tolerated, all subsequent infusions may be delivered over 30 minutes. Do not administer as an intravenous push or bolus.

For more details, refer to the prescribing information at [https://www.gene.com/download/pdf/tecentriq\\_prescribing.pdf](https://www.gene.com/download/pdf/tecentriq_prescribing.pdf).

A hard copy of the atezolizumab prescribing information will be provided to the site in the trial reference manual.

Also refer to the ASCO Practice Guideline on the management of immune-related adverse events in subjects treated with immune checkpoint inhibitor therapy ([Brahmer et al., 2018](#)).

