### **8.1.3 Adverse Event of Special Interest (AESI)**

Immune Mediated Adverse Events (IMAE) and Cardiac events are considered AESIs in the context of this trial.

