#### **Immune-Mediated Adverse Events of Special Interest**

Autoimmune diseases and immune-mediated clinical syndromes, emerging since the initiation of trial product, will be reported as potential IMAEs.

So far, no signal has emerged from the diverse poxvirus constructs studied in the clinic, but the theoretical possibility exists that breaking the immune tolerance to self-antigens may induce autoimmune phenomena. This possibility deserves close vigilance.

The use of PD-1/L1 inhibitors in cancer treatment has expanded rapidly in the last few years. It is imperative that clinicians are knowledgeable about the toxicities associated with these agents, their recommended management and how best to monitor for them. In order to increase awareness, outline strategies and offer guidance on the recommended management of IMAEs in subjects treated with check-point inhibitors, ASCO in collaboration with the National Comprehensive Cancer Network (NCCN) developed clinical practice guidelines (Brahmer et al., 2018) which should be referenced in addition to the mandatory atezolizumab United States Prescribing Information (USPI).

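### The on-study ban on systemic corticosteroids and other immunosuppressants has no exception for treating an immune-mediated adverse event

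*Protocol*

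**What the plan says.** Protocol Section 8.2.2.2 lists six groups of prohibited medication. The last covers systemic corticosteroids and other systemic immunosuppressants, naming among others prednisone, dexamethasone, azathioprine and anti-TNF agents. They are barred "within 2 weeks prior to Day 1 and throughout the trial, or anticipated requirements for systemic immunosuppressive medications during the trial".

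Section 8.2.2.1 sets out what is allowed. Its general rule is "Any medications prescribed for concomitant disease or symptomatic relief of current disease are permitted with the exception of the ones listed in" Section 8.2.2.2. Among its specific allowances is "The use of acute, low-dose, systemic corticosteroid medications (e.g., a one-time dose of dexamethasone for nausea" or premedication before contrast agents.

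On immune toxicity, Section 8.1.3 states: "Immune Mediated Adverse Events (IMAE) and Cardiac events are considered AESIs in the context of this trial". It points to a clinical practice guideline "which should be referenced in addition to the mandatory atezolizumab United States Prescribing Information (USPI"). Section 6.3 does the same: "Also refer to the ASCO Practice Guideline on the management of immune-related adverse events in subjects treated with immune checkpoint inhibitor therapy".

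**The concern.** Atezolizumab is a checkpoint inhibitor, and the protocol expects immune-mediated events closely enough to make them events of special interest. One section sends the site to guidance on managing those events. Another prohibits, for the whole trial and without exception, a drug class that may be needed to manage them.

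The stake is patient safety and clarity of instruction. A site that treats a non-emergency IMAE with systemic immunosuppression above low-dose or replacement levels would, on the text, be giving a prohibited medication. That use could then be recorded among the deviations summarised under SAP Section 4.4.7.3 (an inference; neither document says so). A rule that bears on safety should not depend on each investigator working out which section prevails.

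**Working it through.** There is no design figure to reproduce. The check is whether the ban applies on study, whether any section releases it, and whether the situation is likely to arise.

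**1. The ban applies on study.** The lead-in to Section 8.2.2.2 says the list holds during the trial as well as before Day 1. Four of its six bullets, including this one, extend explicitly through the trial. It is not only a washout rule.

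**2. Search for an exception.**

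| Place | What it provides | Does it release treatment of an IMAE? |
|---|---|---|
| Protocol 8.2.2.1, general permission | Treatment of concomitant disease | No. It yields to the 8.2.2.2 list |
| Protocol 8.2.2.1, specific allowances | Seven items, two on corticosteroids: non-systemic routes and replacement doses; acute low-dose systemic use | No. None of the seven names an IMAE, and none covers the non-steroid immunosuppressants |
| Protocol 4.2 | Departures only for an immediate safety concern | In part. It excuses an urgent departure, but does not clearly reach a non-emergency event |
| Protocol 4.2.5.1 | Stopping the agent responsible for an adverse event; the other may continue | No. It governs trial product, not co-medication |
| Protocol 6.3 and 8.1.3 | Guideline and US prescribing information (USPI) | Not expressly. Neither says it prevails over 8.2.2.2 |
| Protocol 8 | Investigator's duty of appropriate care | Not expressly. It is a general duty |
| SAP | Coding, tables and listings of concomitant medication (4.4.7.7) | No rule on this use |

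**3. Comparison with the entry rule.** Exclusion criterion 25 in Protocol Section 1.4 bars the same drugs "within 2 weeks prior to Day 1, or anticipated requirement for systemic immunosuppressive medications during the trial". Section 8.2.2.2 repeats this almost word for word and adds the on-study extension. As an entry rule it needed no IMAE exception, because Section 8.1.3 defines these events as those "emerging since the initiation of trial product, will be reported as potential IMAEs". Once extended on study, the rule does need one. That the bullet was adapted from the exclusion criterion is an inference; the missing exception does not depend on it.

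**4. Foreseeability.** Section 2.8.1 tells the reader to anticipate the package-insert risks of atezolizumab. Section 2.1 gives two rates from the cited atezolizumab trials:

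- First-line, any IMAE: 12% of 119, so 0.12 × 119 = 14.3, about 14 patients.
- Second-line, Grade 3-4 IMAE: 15/310 = 0.048.

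If these monotherapy rates carried over to the combination at full enrolment (an assumption):

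- Cohort 1, n = 33: expected 33 × 0.12 = 3.96; P(at least one) = 1 − 0.88^33 = 0.985.
- Cohort 2, n = 35: expected 35 × 15/310 = 1.69; P(at least one) = 1 − (295/310)^35 = 0.824.

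The two rates use different grade definitions and cannot be added. They measure how often events occur, not how often immunosuppressants are given. They show only that the conflict between sections is likely to be tested.

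**The case against.** The strongest reply is that the list is not meant to be read so literally. Its first bullet also bars anti-cancer therapy for the whole trial, yet Section 4.2.5.1 anticipates subsequent therapy after progression, and Section 9.6 and SAP Section 4.4.7.9 plan to summarise such therapy. So the period may really mean while on trial product, and a subject who needs immunosuppression can have product stopped under Section 4.2.5.1. This reading is reasonable, but it narrows the gap without closing it: the same section lets the other agent continue after an adverse event attributed to one agent, so a subject can still be on product and need treatment.

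A second reply is that the IMAE provisions are specific and the medication list is general, that the USPI is called mandatory, that investigators must provide appropriate care, and that nothing tells a site to withhold treatment. All of this stands, and it is why the practical impact is limited. It still leaves the site to infer precedence that the protocol does not state.

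Third, the conflict depends on sources the documents do not reproduce. That is correct for the consequence, though not for the missing wording, which can be checked directly. It is also fair that the event rates say nothing about how often steroids are needed; they should not raise the weight of the point.

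Last, an exception alone does not say whether CV301 or atezolizumab is held during immunosuppression. That question is left to Section 4.2.5.1 and the USPI.

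**Conclusion.** The concern holds. Section 8.2.2.2 prohibits systemic corticosteroids and other systemic immunosuppressants on study, and neither document contains an express exception for treating an IMAE. The gap is confined to systemic immunosuppression beyond acute low-dose or replacement use, for events that are not immediate safety concerns.

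Confidence in the missing wording is high. The consequence rests on one assumption from general clinical knowledge: that some IMAEs need such treatment. No number of affected subjects can be given, because the documents report no rate of immunosuppressant use. Type I error, power and the Full Analysis Set are unaffected. The point is worth correcting because the rule, followed as written, gives a worse result than the protocol evidently intends.

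**What to change.** Add to the corticosteroid and immunosuppressant bullet in Protocol Section 8.2.2.2: *except as permitted in Section 8.2.2.1, or when required to treat an immune-mediated adverse event per the atezolizumab USPI and the referenced guideline*.

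The first half also settles a smaller inconsistency: dexamethasone is named as prohibited in Section 8.2.2.2, while a single dose is allowed in Section 8.2.2.1. No change to Section 4.2.5.1 is proposed.

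The cost is one clause. Under Protocol Section 15 it needs a written amendment with IRB approval, so it is best bundled with the next one. The downside is that some subjects will receive immunosuppression on trial. Section 8.2.2 already records the indication, dosage and dates of concomitant medication, and SAP Section 4.4.7.7 already lists it by subject, so no new procedure, data item or analysis is needed.

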### **8.2.3 Physical Examination**

#### Complete physical examination

A complete physical examination will be performed at Screening. The examination includes a review of major organ systems as well as height and weight. The examination should be directed at finding evidence of any infections, tumors and lymphadenopathy. In addition, auscultation of

the heart and lungs to check specifically for signs of any heart condition will be performed. Complete physical exams may be performed at visits other than those indicated based on investigator's discretion.

Any clinically significant findings at the baseline physical examination will be recorded as medical history events, and any new or worsening clinically significant findings post-treatment will be captured as adverse events. The only data captured in the eCRF for the physical examination itself will be the date it was performed.

#### Targeted physical examination

A targeted physical examination, guided by any signs or symptoms previously identified or any new symptoms that the subject has experienced since the last visit, is conducted at visits according to the Trial Procedure Schedule ([Section 1.5](#)) during the Treatment Phase. Clinically significant findings from the treatment period physical examinations will be recorded as AE.

### **8.2.4 Vital Signs**

Vital signs will be measured at visits according to the Trial Procedure Schedule ([Section 1.5](#)). Blood pressure and pulse rate should be obtained after the subject has been seated in an upright position for at least 5 minutes. Vital signs may be assessed at times other than those listed, based on investigator discretion.

### **8.2.5 AEs**

AEs (e.g., feeling of ill-health, subjective symptoms and objective signs, intercurrent diseases, accidents, etc.) observed by the investigator and/or reported by the subject, regardless of relationship to trial product, must be assessed and recorded in the AE eCRF. Only clinically significant findings from the treatment period physical examinations will be recorded as AE.

AEs will be collected and documented at all visits of the active trial phase (including atezolizumab dosing visits) and if ongoing after the active trial phase followed until resolution or until the remote FU visit at the latest.

SAEs and AESIs will be assessed and documented at all trial visits, including the remote FU Visit. Ongoing AESIs and SAEs will be followed up until resolution or achievement of stable clinical conditions.

#### **8.2.5.1 Progression of Underlying Malignancy**

For the purpose of this trial, progression of underlying malignancy is not considered an (S)AE. Hospitalization, prolonged hospitalization, or death due solely to the progression of underlying malignancy will be captured on the AE-section of the eCRF, but may NOT be reported as an

SAE. However, clinical symptoms of progression should be reported as (S)AEs if they cannot be determined to be exclusively due to the progression.

Symptomatic deterioration may occur in the absence of radiographic evidence of tumor progression in some subjects. Alternatively, the disease progression may be so evident that the investigator may elect not to perform further assessments. In such cases, the determination of clinical progression is based on symptomatic deterioration. In these cases, efforts should be made to quantitatively document the progression of the underlying malignancy to the extent possible.

### 8.2.6 Cardiac Assessment

A standard 12-lead ECG will be performed at Screening. ECGs will be evaluated by the investigator for clinical significance. Troponin I will only be measured if clinically indicated.

### 8.2.7 Safety Laboratory Measurements

Safety laboratory (hematology and serum chemistry) is determined at the Screening Visit and at Visits 1-14 while urinalysis is determined at the Screening Visit and Visits 2, 4, 6-14 for all subjects. Thyroid function test (TSH, free T3 and free T4) will be performed at Screening and every 6 weeks through to Visit 14. If clinically indicated, Safety laboratory tests can be performed at any other visit(s). The safety laboratory measurements are performed at the site specific local laboratory. Laboratory normal ranges are provided by the local laboratory and filed in the Regulatory File.

Safety laboratory parameters to be evaluated are in [Table 4](#).

**Table 4: Protocol Required Safety Laboratory Assessments**

Hematology	Biochemistry	Urinalysis
Red blood cell (RBC) count Hemoglobin White blood cell (WBC) count; total and differential Platelet count Hematocrit Mean cell volume (MCV) Mean corpuscular hemoglobin (MCH) Red blood cell distribution width (RDW)	Total protein Albumin Alkaline phosphatase Total bilirubin AST ALT Lactate dehydrogenase (LDH) Creatinine Blood urea nitrogen (BUN) Uric acid Glucose Phosphorous Bicarbonate Chloride Sodium	Specific gravity Protein Glucose Blood Microscopic exam, if abnormal results are noted.

Hematology	Biochemistry	Urinalysis
	Potassium Calcium Amylase Lipase Thyroid Function Test Panel: 
 
• TSH
 
• Free T3
 
• Free T4
 
	

The intensity of laboratory/systemic quantitatively measured toxicities will be graded according to the NCI-CTCAE version 5 toxicity scale in Appendix 2, [Section 17.2](#). In case of other laboratory values not included in the NCI-CTCAE scale the general grading scale below will be used.

Grade 1	Mild; asymptomatic or mild symptoms; clinical or diagnostic observations only; intervention not indicated.
Grade 2	Moderate; minimal, local or noninvasive intervention indicated.
Grade 3	Severe or medically significant but not immediately life-threatening; hospitalization or prolongation of hospitalization indicated.
Grade 4	Life-threatening consequences; urgent intervention indicated.
Grade 5	Death related to AE.

The following parameters will only be evaluated during the Screening Visit for assessment of inclusion/exclusion criteria:

- INR
- PT
- aPTT
- HIV
- HBsAg
- HCV

### 8.2.8 Pregnancy

Women of childbearing potential (WOCBP) and partners of participating males must be using acceptable method of contraceptive measures as outline in [Appendix 1, Section 17.1](#) for 30 days prior to the first vaccination on Day 1, throughout the entire trial and for 5 months after the last dose of atezolizumab. WOCBP subjects will have a pregnancy test (serum or urine) at every visit including atezolizumab infusion only visits which occurs every 3 weeks.

Any pregnancy (participating females and female partners of participating males) that occurs during trial participation must be reported using a clinical trial pregnancy form. To ensure subject

safety, each pregnancy must be reported to BN or designee within 24 hours of learning of its occurrence and should follow the procedures outlined in [Section 8.3.3](#).

